1.5.2 Risks

There are no identified adverse drug reactions for Olpasiran and important potential risks are limited to liver enzyme elevations and hypersensitivity reactions. Olpasiran is an oligonucleotide-based therapy, and events of interest associated with other antisense oligonucleotide (ASO)-based therapies include: effects on platelets and coagulation, immune-inflammatory response, development of anti-drug antibodies, and peripheral neuropathy. Additionally, very low levels of Lp(a) have been associated with increased incidence of type 2 diabetes, but whether pharmacologic lowering of Lp(a) would be associated with an increased risk for development of type 2 diabetes is unknown ^{26, 27}. These risks have not been borne out by either the nonclinical data or clinical data to date for Olpasiran. Safety monitoring measures for these concerns have been implemented in the protocol.

As stated in Section 1.3, no notable trends in safety and tolerability have been observed to date for Olpasiran in two clinical studies in human.

Oligonucleotide-based therapies include ASOs and siRNAs. Key safety concerns associated with these products are further discussed below. Refer to the Olpasiran IB, Section 6.4, for additional information regarding safety concerns with related molecules.

Hypersensitivity Reactions

Administration of any drug may trigger hypersensitivity reactions. Immune-mediated hypersensitivity has been reported with biologics, including systemic and locally restricted reactions (including injection site reactions). ASO based therapies, including siRNAs, do not share molecular similarities with traditional amino acid-based biologics. Nevertheless, double stranded siRNA may be recognized by the innate immune system, triggering innate immune responses²⁸. No hypersensitivity attributed to Olpasiran has been observed to date in clinical trials.

Liver Enzymes Elevation

ASOs, such as mipomersen, have been associated with liver enzyme elevations and hepatic steatosis. Olpasiran-related changes in the liver in the exploratory rat toxicology studies included hepatocellular vacuolation at all dose levels and, at higher dose levels, minimal to mild increased single cell necrosis of hepatocytes sometimes associated with increased mitoses. Hepatocellular mitoses are considered a regenerative response to the single cell necrosis. These liver changes were accompanied by transient, minimal increases in serum alanine aminotransferase (ALT). Minimal to mild increases in serum ALP and bilirubin were also observed. Olpasiran-related changes in the liver were considered to be siRNA platform -related

changes that were not adverse because of their low severity and ultrastructural characteristics. At the doses planned for administration in this study, organ toxicity related to intracellular accumulation is not expected. No safety concern for liver enzyme elevation and Olpasiran has been observed to date in clinical trials.

During the study, safety monitoring based on organ target toxicity and other antisense toxicity²⁹,
³⁰ will be conducted. Safety assessments throughout the study include TEAE and serious TEAE collection; physical examination, including assessment for peripheral neuropathy; monitoring for hypersensitivity reactions; ECGs; laboratory tests, including liver function tests; renal function tests; coagulation and hematologic parameters; metabolic acidosis, if needed; and glucose. Potential anaphylactic reactions will be assessed by Sampson criteria³¹. If Sampson criteria are positive, the potential anaphylactic reaction will be confirmed by measuring tryptase in blood plasma within 30 minutes of symptoms, if feasible.

2. OBJECTIVES AND ENDPOINTS

2.1 Objectives

The primary objective of the study is:

- to evaluate the PK of a single dose of Olpasiran in Chinese subjects with elevated serum Lp(a).

The secondary objectives of the study are:

- to evaluate the safety and tolerability of a single dose of Olpasiran in Chinese subjects with elevated serum Lp(a).
- to evaluate the PD of a single dose of Olpasiran in Chinese subjects with elevated serum Lp(a).

2.2 Endpoints

2.2.1 Primary Endpoints

The primary endpoints of the study are Olpasiran PK parameters:

- C_{max}
- AUC

Additional PK parameters may include, but are not limited to: time to maximum observed concentration (t_{max}), half-life ($t_{1/2}$), apparent volume of distribution during the terminal elimination phase (V_z/F), and apparent total body clearance (CL/F).

2.2.2 Secondary Endpoints

The secondary endpoints of the study are:

- treatment-emergent adverse events (TEAEs)
- clinical laboratory tests
- 12-lead ECGs
- vital signs
- lipids
- serum Lp(a).

3. INVESTIGATIONAL PLAN

3.1 Overall Study Design and Plan

This study is an open-label, randomized, single-dose, parallel-group study in Chinese subjects with elevated serum Lp(a) to assess the PK, safety and tolerability, and PD of Olpasiran.

Subjects will be randomized in a 1:1 ratio to receive a single SC dose of Olpasiran at [REDACTED] mg (Group A) or [REDACTED] mg (Group B). A total of approximately 24 subjects (12 per group) will be enrolled in this study.

Subjects must be living in mainland China, Hong Kong, or Taiwan, and be of Chinese ancestry with an age of 18 to 60 years old (inclusive) and have body mass index of 18 to 32 kg/m² (inclusive) and serum Lp(a) \geq 70 nmol/L (or approximately \geq 27 mg/dL).

Subjects will be assigned to 1 of 2 treatment groups shown in [Table 1](#).

[figure not shown]
Table 1. Treatment Groups

Group	Number of subjects	Dose
A	12	[REDACTED] mg SC
B	12	[REDACTED] mg SC

Abbreviations: SC = subcutaneous.

An overview of the study design is shown in [Figure 1](#). The endpoints are defined in Section [2.2](#).

Figure 1. Study Schematic

AMG 890 Chinese PK Study (N = 24)

Abbreviations: SC = subcutaneous.

Potential subjects will be screened to assess their eligibility to enter the study within 40 days prior to dose administration. Subjects will be admitted into the phase I Clinical Research Unit

(CRU) on Day -1 and be confined to the CRU until discharge on Day 4. Subjects will return to the CRU for outpatient visits on Days 7, 15, 29, 57, 85, 113, 155, and 183, and at the end of study (EOS) visit on Day 225. A telephone visit will be scheduled for TEAE assessments on Day 211. The total duration of study participation for each subject (from Screening through EOS visit) is anticipated to be approximately 265 days (about 38 weeks).

The start of the study is defined as the date the first subject signs an Informed Consent Form (ICF). The point of enrollment occurs at the time of subject randomization number allocation. The enrollment date is the same as the randomization date. The EOS for overall study is defined as the date of the last subject's last assessment (scheduled or unscheduled).

A Schedule of Assessments is presented in [Appendix 9](#).

3.2 Discussion of Study Design

This study will be open-label.

Conducting the study in subjects with elevated serum Lp(a) in Chinese subjects is necessary to support a comparison of Olpasiran PK parameters with those observed in the FIH study (20170544) and therefore to assess the ethnic difference, as baseline Lp(a) levels may impact Olpasiran exposure and the interpretation of these analyses.

3.3 Selection of Doses in the Study

The selection of the doses for this study are supported by the dose margins determined from the NOAEL in rat and cynomolgus monkey (150 mg/kg). [REDACTED]

[REDACTED]. These calculated dose margins are conservative as only a single dose will be given in this study, and the NOAEL was determined based on data from every 4-week dosing (x3) in rat and cynomolgus monkey repeat-dose toxicology studies.

The preliminary data from the FIH study (20170544) and the Japanese phase 1 PK study (20180222) indicated that Olpasiran is rapidly absorbed and eliminated with low, but detectable serum exposures, as expected for a siRNA oligonucleotide. Given the hepatic site target and rapid elimination of Olpasiran from systemic circulation, the dose-response relationship related to reductions in Lp(a) were used to support dose selection in this study and for future studies. The preliminary PD data demonstrated effective lowering of Lp(a) levels across the evaluated dose range of [REDACTED] mg and [REDACTED] mg, and with no identified safety concerns.

In this study, the [REDACTED] and [REDACTED] mg SC doses are selected to evaluate the PK, PD, safety, and tolerability of Olpasiran in Chinese subjects with elevated serum Lp(a) levels. [REDACTED]

Evaluation of these 2 dose levels in the current study will allow a direct comparison of Olpasiran PK and Lp(a) reductions with those observed in FIH Study (20170544) in subjects with same screening Lp(a) levels ≥ 70 nmol/L. [REDACTED]

[REDACTED]

[REDACTED]

Therefore, the dose margins, the FIH study results, and the PK study in Japanese subjects support the selection of the dose levels to be evaluated in this study to assess the PK, PD, safety, and tolerability of Olpasiran, and to evaluate the magnitude and durability of Lp(a) reduction in Chinese subjects with elevated serum Lp(a).

3.4 End of Study

Primary Completion: The primary completion date is defined as the date when the last subject is assessed or receives an intervention for the final collection of data for the primary endpoints (see Section 2.2.1), whether the study concluded as planned in the protocol or was terminated early.

The primary completion date is the date when the last subject has completed the assessments on Day 225 of the study.

If the study concludes prior to the primary completion date originally planned in the protocol (i.e., early termination of the study), then the primary completion will be the date when the last subject is assessed or receives an intervention for evaluation in the study (i.e., last subject last visit).

End of Study: The EOS date is defined as the date when the last subject across all sites is assessed or receives an intervention for evaluation in the study (i.e., last subject last visit), after any additional parts in the study (e.g., long-term follow-up), as applicable.

4. SELECTION OF STUDY POPULATION

4.1 Inclusion Criteria

Inclusion eligibility criteria will be evaluated in 2 parts during the screening period:

- **Part 1:** After written informed consent is obtained, subjects will provide a blood sample for a preliminary Lp(a) assessment to determine eligibility for Part 2 screening. Subjects with Lp(a) \geq 70 nmol/L (or approximately \geq 27 mg/dL) will be eligible to return to the CRU for Part 2 screening. Subjects not eligible to return for Part 2 screening will be screen failed.
- **Part 2:** Eligible subjects will complete all remaining screening procedures and tests that establish eligibility within 40 days prior to the Day 1 visit.

To be eligible for the study, subjects must provide written informed consent to participate and must fulfill the following criteria:

Inclusion Criteria (Part 1)

1. Subject has provided informed consent before initiation of any study-specific activities/procedures.
2. Must be a resident in mainland China, Hong Kong, or Taiwan, and of Chinese ancestry.
3. Male or female subjects, between 18 and 60 years of age (inclusive) at the time of Screening.
4. Screening serum Lp(a) \geq 70 nmol/L (or approximately \geq 27 mg/dL).

Inclusion Criteria (Part 2)

1. In good health, determined by no clinically significant findings from medical history, physical examination, 12-lead ECG, vital sign measurements, and clinical laboratory evaluations (congenital nonhemolytic hyperbilirubinemia [e.g., suspicion of Gilbert's syndrome based on total and direct bilirubin] is not acceptable) as assessed by the Investigator (or designee).
2. Body mass index between 18 and 32 kg/m² (inclusive) at the time of Screening.
3. Subjects who are on statin must be on a stable dose of the same statin for at least 6 weeks prior to enrollment, and plan to remain on a stable dose (i.e., no change in medication or dosage) for the duration of the study
4. Females must be of non-reproductive potential:
 - a. Postmenopausal defined as:
 - i. Age of \geq 55 years with no menses for at least 12 months; OR
 - ii. Age of $<$ 55 years with no menses for at least 12 months AND with a follicle stimulating hormone (FSH) level $>$ 40 IU/L or according to the definition of "postmenopausal range" for the laboratory involved; OR
 - b. History of hysterectomy; OR
 - c. History of bilateral oophorectomy

4.2 Exclusion Criteria

Subjects will be excluded from the study if they satisfy any of the following criteria prior to enrollment unless otherwise stated:

1. History or clinical evidence of peripheral neuropathy.
2. Currently receiving apheresis as lipid reducing therapy.
3. History or clinical evidence of bleeding diathesis or any coagulation disorder, including prothrombin time (PT), activated partial thromboplastin time (APTT), or platelet count outside of the laboratory's normal reference range at screening. Subjects with PT and/or APTT values that are outside of the laboratory's normal reference range at screening may still be eligible to proceed to enrollment if the results are judged by the investigator in consultation with the study medical monitor to not be clinically significant.
4. History or clinical evidence of diabetes mellitus, including a fasting glucose ≥ 125 mg/dL (6.9 mmol/L) at Screening.
5. History or evidence, at Screening or Check-in, of clinically significant disorder, condition, or disease not otherwise excluded that, in the opinion of the Investigator (or designee), would pose a risk to subject safety or interfere with the study evaluation, procedures, or completion.

Exceptions include:

- a. Subjects with controlled and stable arterial hypertension. Controlled and stable hypertension with a systolic blood pressure [BP] < 150 mmHg or diastolic BP < 90 mmHg at Screening and Day -1, with no change in medication and dosage for at least 8 weeks prior to enrollment and expected to remain on this dose and medication for the entire duration of the study. If the initial BP is elevated, the reading may be repeated again at least 15 minutes later and the lower of the 2 readings may be used.
- b. Subjects with diagnosis of hyperlipidemia on treatment with a stable dose of the same statin (with or without concomitant ezetimibe) for at least 6 weeks prior to enrollment and expected to remain on this dose and medication for the entire duration of the study.
6. A QT interval corrected for HR based on the Fridericia correction (QTcF) interval > 450 msec in male subjects or > 470 msec in female subjects or history/evidence of long QT syndrome, at Screening.
7. Subject has known sensitivity to any of the products or components to be administered during dosing.
8. Estimated glomerular filtration rate (eGFR) less than 60 mL/min/1.73 m² as calculated by the Modification of Diet in Renal Disease (MDRD) equation, at Screening.
9. Alanine aminotransferase (ALT) or aspartate aminotransferase (AST) $> 1.1 \times$ upper limit of normal (ULN), at Screening or Check-in. For subjects on a stable dose of statin, ALT or AST $> 1.5 \times$ ULN of the laboratory's reference at Screening or Check-in.

10. Positive hepatitis B or hepatitis C panel and/or positive human immunodeficiency virus antibodies test at Screening. Subjects whose results are compatible with prior immunity (vaccination or prior recovered infection) may be included.
11. Use of any over-the-counter or prescription medications within 14 days or 5 half-lives (whichever is longer) before dosing on Day 1 and during the study is not permitted, unless to treat a TEAE. Continued use, if applicable, will be reviewed by the Principal Investigator (or designee) and in consultation with the Sponsor. Written documentation of this review and Sponsor acknowledgement is required for subject participation. Exceptions are:
 - a. Acetaminophen (paracetamol) up to 2 g per day for analgesia
 - b. Hormone replacement therapy (e.g., estrogen, thyroid) provided the subject is stable on replacement therapy
 - c. Medication for the management of arterial hypertension, including, but not limited to, angiotensin-converting enzyme inhibitors, angiotensin receptor blockers, beta blockers, calcium channel blockers, or low dose thiazides, provided it is stable (i.e., no change in drug or dose) for at least 8 weeks prior to enrollment
 - d. Use of anti-platelet therapy (low-dose acetylsalicylic acid [up to 162.5 mg daily], clopidogrel, or ticagrelor) is allowed, provided subjects have been on a stable dose for at least 6 weeks prior to enrollment and plan to be on the same dose for the duration of the study
 - e. If subjects are on a statin, subjects must be on a stable dose of the same statin for at least 6 weeks prior to enrollment, and plan to remain on the same dose (i.e., no change in medication or dosage) for the duration of the study
 - f. Use of ezetimibe is allowed, provided subjects have been on a stable dose for at least 6 weeks prior to enrollment and plan to be on the same dose for the duration of the study
 - g. Medication used to manage chronic conditions not excluded by other exclusion criteria, provided subjects have been on a stable dose for at least 6 weeks prior to enrollment and plan to be on the same dose for the duration of the study. Medication must be reviewed and approved by the Investigator (or designee) and acknowledged by the Sponsor. Written documentation of this review and Sponsor acknowledgement is required for subject participation.
12. Subjects are on niacin, or have received niacin > 200 mg/day within 3 months prior to dosing on Day 1.
13. Use of any herbal medicines, vitamins or dietary supplements known to affect lipid metabolism (e.g., fish oils > 1000 mg/day, red yeast rice extract), within 30 days prior to dosing on Day 1 and for the duration of the study.
14. All herbal medicines (e.g., St. John's wort) and dietary supplements (with the exception of those known to affect lipid metabolism, which are excluded above) consumed by the subject within the 30 days prior to Check-in, unless deemed acceptable by the Investigator (or designee) and in consultation with the Sponsor.
15. Triglycerides \geq 5.65 mmol/L (i.e., 500 mg/dL) at Screening
16. History of drug/chemical abuse within 1 year prior to Check-in.
17. Alcohol consumption within 48 hours prior to Check-in and during in-house residency period.

18. Alcohol consumption of > 14 units per week for males and > 7 units per week for females. One unit of alcohol equals 12 oz (360 mL) beer, 1½ oz (45 mL) liquor, or 5 oz (150 mL) wine.
19. Positive test for illicit drugs and/or alcohol use at Screening or Check-in.
20. Female subjects with a positive pregnancy test at Screening or Check-in.
21. Female subjects lactating/breastfeeding or who plans to breastfeed during the study through 90 days after Olpasiran dosing.
22. Unwilling to abstain from sperm donation through 90 days after Olpasiran dosing (see [Appendix 4](#)).
23. Male subjects with a female partner of childbearing potential and not willing to inform his partner of his participation in this clinical study.
24. Male subjects with a pregnant partner or partner planning to become pregnant while the subject is on study through 90 days after Olpasiran dosing.
25. Subject has received a dose of an investigational drug within the past 30 days or 5 half-lives, whichever is longer, prior to Check-in. Other investigational procedures while participating in this study are excluded.
26. Have previously completed or withdrawn from this study or any other study investigating Olpasiran or have previously received the investigational product.
27. Donation of blood from 60 days prior to Check-in, plasma from 2 weeks prior to Check-in, or platelets from 6 weeks prior to Check-in.
28. Performed strenuous exercise within 72 hours prior to Screening or Check-in.
29. Unwilling to abide with study restrictions.
30. Subjects who, in the opinion of the Investigator (or designee), should not participate in this study.

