1.5.1 Key Benefits

Subjects in the current study will not receive any health benefit (beyond that of an assessment of their medical status) from participating in the study.

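### The controlled-hypertension exception joins its two blood pressure limits with *or*, so one component under its limit is enough

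*Protocol*

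**What the plan says.** Protocol Section 4.2, criterion 5, excludes anyone with a clinically significant disorder that the investigator thinks would endanger the subject or disturb the study. Exception a to that criterion is headed "Subjects with controlled and stable arterial hypertension". It then gives the pressure such a subject may have: "systolic blood pressure [BP] < 150 mmHg or diastolic BP < 90 mmHg at Screening and Day -1". Two further conditions follow. Treatment must be steady, "with no change in medication and dosage for at least 8 weeks prior to enrollment", and it must be expected to stay so for the whole study. If the first reading is high, it may be repeated after at least 15 minutes and the lower of the two used.

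Two other criteria bear on blood pressure without giving a figure. Part 2 inclusion criterion 1 (Section 4.1) requires the subject to be "In good health, determined by no clinically significant findings from medical history, physical examination, 12-lead ECG, vital sign measurements", as well as from laboratory results, as assessed by the investigator. Exclusion 30 removes "Subjects who, in the opinion of the Investigator (or designee), should not participate in this study".

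**The concern.** The exception is meant for hypertension under control, but its limits are joined by *or* in a statement of what is allowed. In an exclusion, *or* tightens the rule, because either breach removes the subject. In a permission it loosens the rule, because meeting either limit is enough. A subject with one component well above its limit therefore satisfies the BP condition as long as the other is below, which is hard to square with the word controlled.

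What is at stake is subject protection and consistent screening. Section 1.5.1 says "Subjects in the current study will not receive any health benefit" beyond an assessment of their medical status, so an unambiguous entry limit is a reasonable minimum. One monitor could accept a mixed reading on the text, while another recorded it as a deviation on the presumed intent.

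**Working it through.** **Inputs.** From Protocol 4.2, criterion 5 exception a: systolic limit 150 mmHg, diastolic limit 90 mmHg, connective *or*, applied at Screening and at Day -1. The readings below are illustrative and do not come from the documents. The 8-week medication condition is taken as met. The plan gives no figure on this point, so there is none to reproduce.

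**The rule as written and as probably meant.** Let S be systolic and D diastolic, in mmHg.

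- As written: pass if S < 150 *or* D < 90. The negation is S ≥ 150 *and* D ≥ 90, so a subject fails only when both components are at or above their limits.
- With *and*: pass if S < 150 *and* D < 90. A subject fails when either component is at or above its limit.
- The two rules disagree exactly when one component is below its limit and the other is not.

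| Reading | S < 150 | D < 90 | As written (*or*) | With *and* |
|---|---|---|---|---|
| 145/85 | yes | yes | pass | pass |
| 145/95 | yes | no | pass | fail |
| 152/85 | no | yes | pass | fail |
| 145/115 | yes | no | pass | fail |
| 185/85 | no | yes | pass | fail |
| 155/95 | no | no | fail | fail |

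As written, the rule turns away 155/95 but passes 185/85, whose systolic pressure is 185 − 155 = 30 mmHg higher. It also passes 145/115, whose diastolic pressure is 115 − 95 = 20 mmHg higher.

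**Does other text supply the missing conjunction?**

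- The remaining conditions in exception a concern medication, not the level of pressure.
- The repeat-reading rule (exception a, and again in Section 7.1.1) allows the lower of two readings. It does not require both components to be under their limits.
- Exclusion 11, exception c, asks only that antihypertensive treatment be stable.
- Section 7.6.4 (Vital Signs) sets no entry limit.
- SAP Section 8.6.3 covers listing and summarising vital signs, not eligibility.
- The change summaries for Protocol versions 2.0 and 3.0, as shown, do not touch this exception.

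**The protocol's own usage.** Exclusion 9 uses *or* correctly: a subject is removed if either ALT or AST is too high. Where two conditions must both hold, the protocol says so. For women under 55, Section 4.1 requires "with no menses for at least 12 months AND with a follicle stimulating hormone (FSH) level" above 40 IU/L.

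**The case against.** The best defence has three parts.

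First, the sentence does not strictly say that controlled hypertension is defined by these figures. It speaks of controlled and stable hypertension *with* such a pressure, so 185/85 could be said to fail at the word controlled before the limits are reached. That reading is possible. But the protocol gives controlled no other meaning, so the sentence is at best ambiguous.

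Second, satisfying exception a does not make anyone eligible. It lifts only exclusion 5. The good-health criterion still has to be met and covers vital signs, exclusion 30 remains, and Section 7 allows no waivers. This stands as far as it goes: a reading such as 185/85 would very probably be stopped. Meeting the good-health criterion is mandatory, but whether a reading is clinically significant is left to the investigator, and no figure is set. For 152/85 or 145/95 that judgement could go either way, and a numeric limit is there to settle such cases.

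Third, the documents show no blood pressure hazard from the drug. Monkey safety pharmacology found no BP change up to 150 mg/kg. The first-in-human study showed no notable vital-sign trends, and the Japanese study no pattern of important vital-sign abnormalities. Subjects receive one dose and stay in the unit to Day 4. This limits the likely harm, but it does not make the criterion right.

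It is also fair to say that divergence between sites is conjecture, since the number of sites is not stated.

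**Conclusion.** The concern holds. As worded, the BP condition passes every subject with only one component under its limit, and it is the only numeric BP entry limit in either document. It should be corrected, though it does not threaten the trial's conclusions: no PK endpoint, sample-size statement or planned analysis depends on it.

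The practical reach is the set of mixed readings, chiefly borderline ones. Its size cannot be derived, because the documents give no BP distribution for the screened population. The conclusion rests on the literal text. That *and* was intended is an inference from the word controlled and from the drafting elsewhere; nothing in the documents states it.

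**What to change.** In Protocol Section 4.2, criterion 5 exception a, replace *or* with *and*: systolic BP < 150 mmHg and diastolic BP < 90 mmHg, with both to be met at Screening and at Day -1. Leave the 8-week stability condition and the repeat-reading rule as they are.

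The change is one word, with possibly a few more screen failures. It is of the same kind as the correction in version 3.0 to the glucose unit in the neighbouring criterion 4. The SAP needs no change. If enrolment has already closed, which the documents do not state, the vital-signs listings planned in SAP Section 8.6.3 can be checked for hypertensive entrants with one component at or above its limit at Screening or Day -1.
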